3.2 Sample Size Considerations

There is no formal sample size calculation for this small phase I/II study and no formal hypothesis testing will be performed. A sample size of 20 participants was chosen to ensure that it is financially feasible to conduct the study and logistically possible to complete the study enrollment within the study period. The primary objective is to assess the safety and feasibility of the stem cell therapy; however, it is desired to obtain some gauge of potential efficacy of this cell therapy. Thus, participants will be randomized 1:1 to immediate cellular therapy/deferred sham or immediate sham/deferred cellular therapy. After their first treatment (cellular or sham), participants will be followed for 6 months, at which time participants who initially received sham treatment will be given stem cell treatment and vice versa. The small sample size is not ideal, but for practical purposes, it would be difficult to increase the sample size significantly without increasing the enrollment period for the study.

Although the study as designed may not be large enough to determine efficacy, some efficacy signals might be observed with the current study design. Such a signal may warrant further investigation of this therapy for CRVO. When a phase II/III randomized controlled trial is planned, appropriate sample size calculations will be performed.

It is recognized that the study has limited power to show efficacy; however, we hope to obtain some trends in change in visual function or retinal morphology or perfusion that may suggest efficacy to justify a larger randomized prospective clinical trial. Power calculations are explored in section 5.2.2 for the proposed method of analyzing the secondary outcomes.

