Based on the observations of the preliminary phase 1 clinical trial, we anticipate any improvement in visual function associated with study cell therapy to occur within 3 months of cell therapy and for any effect to be sustained over time (but not increasing over time).⁵ Due to small sample sizes, it is recognized that there is limited power to detect differences (Appendix), but trends may be identified that would encourage future trials of this treatment, provided no safety concerns are found. Significance testing will use 2-sided tests with alpha=0.05. No adjustment for multiple comparisons will be made as these are purely exploratory analyses for hypothesis generation.

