7.3.1.2 Effect of Cellular Therapy Over Time

The mean change from baseline at 1, 3 and 6 months post-cellular therapy will be assessed in both treatment arms. Comparisons will be made between the two arms to identify any differences in the effect of cellular therapy. If there are no statistically significant differences identified, the treatment arms will be combined, and a within-patient paired t-test will be performed. If a statistically significant difference is found, within-patient paired t-tests will be performed separately in each treatment arm to assess the effect of cellular therapy. Additionally, the effect of cellular therapy will be assessed in the immediate cellular therapy/deferred sham therapy arm at 12 months compared to the screening visit with a within-patient paired t-test.

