13.0 APPENDIX

13.1 Simulation Results

Simulations were used to produce power curves for the independent t-test. The following plots show the power curves for using the t-test in different scenarios with varying degrees of treatment decay and period effect in the simulated data. Treatment decay is defined as the attenuation of cellular treatment, which might be observed in the immediate cellular therapy/deferred sham therapy group during Study Period 2. Period effect is defined as the effect on treatment of being in Study Period 1 versus being in Study Period 2. Estimates of participant level random effects and measurement error used in these power calculations were derived from visual acuity data in the Study of Comparative Treatments for Retinal Vein Occlusion 2 (SCORE 2)⁷.

FIGURE 1 shows the power curve when estimating treatment effect of visual acuity (i.e., difference in number of letters read) holding treatment decay and period effect at 0.

Figure 1: Power Curve for T-test

Standard deviation of the patient level random effect=15 Standard deviation of the measurement error=6.2 Treatment decay (Q)=0 Period effect (T)=0 **FIGURE 2** and **FIGURE 3** show the power of estimating treatment effect of visual acuity while introducing treatment decay and a period effect, respectively.

Figure 2: Power Curve with Differing Levels of Treatment Decay

Figure 3: Power Curve with Differing Levels of Period Effect

Figures 2 and 3 show that treatment decay and a period effect do not affect power. The overall conclusion is that power to detect a treatment effect does not approach even 70% until the treatment effect is quite large (difference of 20 letters read).

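### SAP 7.3.1.2 lets a significance test of about 10 versus 10 participants decide whether the arms are pooled, which distorts arm-specific conclusions about the cells

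*SAP*

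**What the plan says.** SAP 7.3.1.2 assesses the change from baseline at 1, 3 and 6 months after cells in both arms. For the deferred arm, SAP 4.2.2 makes the Month 6 visit the baseline. The section then states: "Comparisons will be made between the two arms to identify any differences in the effect of cellular therapy". It does not name the test. Two conditional sentences follow. The first is "If there are no statistically significant differences identified, the treatment arms will be combined, and a within-patient paired t-test will be performed". The second is "If a statistically significant difference is found, within-patient paired t-tests will be performed separately in each treatment arm". No similarity margin is given, and the section does not ask for the between-arm difference to be reported with its uncertainty. The 12-month paired test in the immediate-cell arm stands outside this rule.

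Other parts of the plan bear on the point:

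- SAP 7.3 sets the level: "Significance testing will use 2-sided tests with alpha=0.05". It also concedes limited power, makes no multiplicity adjustment and calls the analyses exploratory.
- SAP 3.2 says that no formal hypothesis testing will take place. Protocol 7.8.2.2 restricts P-values to indicating strength of association and rules out their use for hypothesis testing.
- SAP 13.1 allows for the arms to differ: "Period effect is defined as the effect on treatment of being in Study Period 1 versus being in Study Period 2".
- SAP 7.3, item 1, requires descriptive tables of change by arm, period and visit for every continuous outcome on the pre-selected list, whatever the comparison shows.

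**The concern.** The rule turns a P-value into a switch. A result above 0.05 leads to one paired t-test presented for both arms together; a result below 0.05 leads to two. With about 10 participants per arm, a result above 0.05 is what one expects even when the arms differ materially. A difference is also conceivable: the deferred arm receives cells six months later and is measured from a different baseline.

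Two errors are possible. A missed difference lets a significant pooled result be credited to an arm in which cells did nothing. A chance significant comparison splits the arms and displays a difference that is large because it was selected for being large. The stated purpose of these outcomes is to look for trends that would justify a larger trial, so the rule for choosing the inferential result matters even though the work is exploratory.

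**Working it through.** **Inputs**

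- Sample size (SAP 3.2): "A sample size of 20 participants was chosen to ensure that it is financially feasible to conduct the study". With 1:1 allocation (same section), this gives 10 per arm. No dropout is assumed; 9 and 8 per arm are shown as a check.
- Two-sided alpha 0.05 (SAP 7.3).
- Test: independent t-test. This is inferred from SAP 7.3.1.1 and 13.1, because 7.3.1.2 names none.
- SD components for visual acuity (SAP 13.1): 15 letters between patients and 6.2 letters measurement error.
- True difference between arms in the effect of cells: not in the documents. It is expressed below as d, in SDs of the change score, over a range.

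**The plan's own power figure.** SAP 13.1 says that power for visual acuity does not approach 70% until the difference is about 20 letters. That figure concerns cells against sham. The single-visit SD is √(15² + 6.2²) = 16.23. At 20 letters, d = 20/16.23 = 1.23, and noncentral-t power on 18 df is 74.1%; at 19 letters it is 69.7%. The verbal threshold is consistent with these inputs. The SAP gives no power figure for the comparison that decides pooling.

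**Power of the comparison that decides pooling.** The noncentrality is d/√(1/10 + 1/10) = d/0.447, with 18 df and critical value 2.101.

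| d (SD of change) | Power | Missed, so pooled |
|---|---|---|
| 0.25 | 8.3% | 91.7% |
| 0.5 | 18.5% | 81.5% |
| 0.75 | 35.5% | 64.5% |
| 1.0 | 56.2% | 43.8% |
| 1.5 | 88.7% | 11.3% |

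Power of 80% needs d = 1.32. At d = 0.5 the miss rate is 83.0% with 9 per arm and 84.6% with 8. If the patient effect cancels in the change score (an assumption), its SD is 6.2 × √2 = 8.77 letters. Then 0.5 SD is 4.4 letters, and 1.32 SD is 11.6 letters.

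**The two-step rule.** It was simulated with 200,000 trials per scenario: normal changes, equal SDs, 10 per arm. After a non-significant comparison, a one-sample t-test is run on all 20 changes; after a significant one, a separate one-sample t-test is run on each arm's 10 changes.

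*Target: the average effect over the two arms.* If a 95% interval is attached to the pooled analysis, its coverage given pooling is 95.0% at d = 0, 95.5% at d = 0.5 and about 96.5% at d = 1. The pooled test is not anti-conservative for this target.

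*Target: an arm in which cells do nothing.* The probability that the reported test covering that arm is significant is P(pool) × P(pooled test significant, given pool) + P(split) × P(that arm's own test significant, given split).

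| Effect in the other arm | Two-step rule | Always separate |
|---|---|---|
| 0 | 6.4% | 5.0% |
| 0.25 SD | 9.3% | 5.1% |
| 0.5 SD | 16.3% | 5.0% |
| 1.0 SD | 24.8% | 5.0% |

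*Chance splits.* When the arms truly agree, the comparison still splits them 5% of the time. Significance requires an observed difference of at least 2.101 × √0.2 = 0.94 pooled sample SDs. In the simulation, the apparent difference in these splits averages 0.99 SD, or about 0.99 × 8.77 = 8.7 letters.

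**Precision of the alternative.** The arm-stratified average is the mean of the two arm means, with half-width t(0.975; 18) × s_within/√20. Its coverage is 95.1%, 95.0% and 94.9% at d = 0, 0.5 and 1. Its expected half-width is 0.463 SD, against 0.462 SD for simple pooling when the arms agree. In trials where the rule would pool despite a true 1-SD difference, the half-widths are 0.486 and 0.498 SD respectively.

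**The case against.** The strongest reply is that little is hidden. SAP 7.3, item 1, already tabulates change by arm and visit for each continuous outcome on the pre-selected list, and 7.3.1.2 itself looks at both arms before the switch applies. SAP 4.3 lists n, mean and SD among the descriptive statistics, so a reader could compute the arm difference and an interval. This stands, and it limits the point to which inferential result is reported. It rules out the broader inference that what a reader sees of each arm is left to chance.

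Three other inferences go beyond the documents. First, a reader might conclude that the intervals following the switch are not 95% intervals. SAP 7.3.1.2 plans paired t-tests and no intervals, and an interval attached to the pooled result would hold its level for the average effect. Second, a reader might say that the SAP takes non-significance as proof of equal effect. It says no such thing and concedes low power; the fair statement is that non-significance is its only condition for pooling. Third, a reader might assume a fresh decision at each visit, with one outcome pooled at month 1 and split at month 3. The SAP does not say whether the decision is per visit or per measure, and the separate table-shell document it refers to is not available here.

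It is also fair to say that small arm differences are the plan's working case. Both arms get the same therapy, the protocol (Section 4.0) describes the condition as typically acute and non-progressive, and SAP 4.2.2 expects the sham arm's two baselines to be similar. At 0.25 SD the error for a zero-effect arm is 9.3%, a modest excess. But this is expectation, and a comparison with 8.3% power at that difference cannot confirm it.

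The exploratory label lowers the stakes without removing the flaw. If P-values are not for hypothesis testing, they should not select the analysis.

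**Conclusion.** The point holds for arm-specific inference on exploratory secondary outcomes. The comparison that decides pooling misses a 0.5-SD difference about 81% of the time. The two-step rule then raises the chance of declaring an effect that covers a zero-effect arm from 5% to about 16%, or to about 25% when the other arm's effect is 1 SD. A chance split shows an apparent difference near 1 SD where there is none. The pooled test remains valid for the average effect over both arms, and the primary safety and feasibility outcomes are untouched. The rule is also inconsistent with SAP 3.2 and Protocol 7.8.2.2, whatever effect size one assumes.

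The sizes rest on 10 completers per arm, normal changes with equal SDs, an independent t-test for the unnamed comparison, and effect sizes that the documents do not supply. The change is worth making before analysis because it is cheap.

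**What to change.** Delete the two conditional sentences in SAP 7.3.1.2. For each measure listed for this analysis, at 1, 3 and 6 months after cells, always report:

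- (a) each arm's mean change with a 95% confidence interval;
- (b) the between-arm difference in change with a 95% confidence interval;
- (c) one arm-stratified average: the equal-weight mean of the two arm means, using the pooled within-arm variance, on 18 df with 10 per arm (in general, the two arm sizes summed minus 2).

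Add a sentence saying that a non-significant or wide result in (b) is not evidence that cells had the same effect in both arms. The separate 12-month analysis in the immediate-cell arm can stay as it is.

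The cost is SAP wording and a few more table columns. No new data are needed, and the loss of precision when the arms agree is 0.001 SD in half-width (0.463 against 0.462).

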7.3.2 Secondary Efficacy Outcome Measures

The sections below provide a summary of individual outcome measures, parameters (e.g., mean, mean change), timepoints and analyses that will be performed for each efficacy outcome. Analyses for treatment effect and effect of cellular therapy are described in Sections 7.3.1.1 and 7.3.1.2, respectively. Outcomes will be examined in the study eye unless otherwise noted.

7.3.2.1 Changes in Visual Acuity

Best corrected visual acuity (BCVA) of the study eye will be obtained at all scheduled study visits by a certified visual acuity examiner using ETDRS visual acuity chart and refraction. Table 3 outlines the outcome analyses that will be performed for visual acuity.

Table 3: Visual Acuity Outcomes				
Outcome Measure	Parameter	Timepoints	Analyses	
ETDRS Visual Acuity	Mean, mean change	All visits	Descriptive	
Letter Score	from baseline	1, 3 and 6 months following Treatment 1	Treatment effect	
		1, 3 and 6 months post- cellular therapy in both arms; 12 months post-cellular therapy in immediate cell/deferred sham arm	Effect of cellular therapy over time	
ETDRS Visual Acuity Improvement and Losses	Categorical change: Decrease by ≥ 10 letters/within 9 letters/improve by ≥ 10 letters; Decrease by ≥ 15 letters/within 14 letters/improve by ≥ 15 letters	All visits	Descriptive	

7.3.2.2 Changes in Microperimetry

Microperimetry will be used as another measure of macular function and to gauge safety and potential efficacy of the study treatment. Table 4 outlines the outcome analyses that will be performed for microperimetry. Categorical versions of continuous variables may also be explored.

Table 4: Microperimetry Outcomes				
Outcome Measure	Parameter	Timepoints	Analyses	
% Reduced Sensitivity Average Threshold	Mean, mean	All visits	Descriptive	
	change from baseline	1, 3 and 6 months following Treatment 1	Treatment effect	
		1, 3 and 6 months post- cellular therapy in both arms; 12 months post- cellular therapy in immediate cell/deferred sham arm	Effect of cellular therapy over time	

7.3.2.3 Changes in OCT/OCTA

As a secondary outcome measure and a measure of change in macular morphology, OCT image analysis will be performed. Table 5 outlines the outcome analyses that will be performed for OCT/OCTA. Categorical versions of continuous variables may also be explored.

Table 5: OCT/OCTA Outcomes					
Modality	Outcome Measure	Parameter	Timepoints	Analyses	
ОСТ	Macular Thickness by ETDRS zone	Mean change from baseline	All visits	Descriptive	
	Macular thickness in ETDRS Zone 1 (Central)	Mean change from baseline	1, 3 and 6 months following Treatment 1	Treatment effect for central macular thickness	
			1, 3 and 6 months post-cellular therapy in both arms; 12 months post-cellular therapy in immediate cell/deferred sham arm	Effect of cellular therapy over time for central macular thickness	
	Macular Volume	Mean change from	All visits	Descriptive	
		paseline	1, 3 and 6 months following Treatment 1	Treatment effect	

Table 5: OCT/OCTA Outcomes				
Modality	Outcome Measure	Parameter	Timepoints	Analyses
			1, 3 and 6 months post-cellular therapy in both arms; 12 months post-cellular therapy in immediate cell/deferred sham arm	Effect of cellular therapy over time
	Average Macular Thickness	Mean change from baseline	All visits	Descriptive
	Presence of CME	Count, percentage, change from baseline	All visits	Descriptive
	Presence of Subretinal Fluid	Count, percentage, change from baseline	All visits	Descriptive
	Photoreceptor Layer (IS/OS Junction)	Count, percentage, change from baseline	All visits	Descriptive
	Photoreceptor Layer (ELM)	Count, percentage, change from baseline	All visits	Descriptive
	Presence of hyper-reflective foci in vitreous, intraretinal and subretinal	Count, percentage	All visits	Descriptive
	Number of hyper- reflective foci in vitreous, intraretinal and subretinal	Mean change from baseline	All visits	Descriptive
	Length of longest DRIL in line scans	Mean change from baseline	All visits	Descriptive
	Presence of ERM	Count, percentage, change from baseline	All visits	Descriptive
	Presence of VMT/VMA	Count, percentage, change from baseline	All visits	Descriptive
OCTA	Foveal avascular	Mean change from	All visits	Descriptive
		Daselline	1, 3 and 6 months following Treatment 1	Treatment effect
			1, 3 and 6 months post-cellular therapy in both arms; 12	Effect of cellular therapy over time

Table 5: OCT/OCTA Outcomes				
Modality	Outcome Measure	Parameter	Timepoints	Analyses
			months post-cellular therapy in immediate cell/deferred sham arm	
	Automated	Mean change from	All visits	Descriptive
	Deep Vascular Density (VD) by ETDRS zone	baseline	1, 3 and 6 months following Treatment 1	Treatment effect for central, whole image 3.0mm scan, and whole image 6.0mm scan
			1, 3 and 6 months post-cellular therapy in both arms; 12 months post-cellular therapy in immediate cell/deferred sham arm	Effect of cellular therapy over time for central, whole image 3.0mm scan, and whole image 6.0mm scan
	VD analysis of superficial plexus and deep plexus	Count, percentage	All visits	Descriptive
	Number of microaneurysms in total ETDRS area	Mean change from baseline	All visits	Descriptive
	Number of telangiectasia in total ETDRS area	Mean change from baseline	All visits	Descriptive
	RNFL Thickness;	Mean change from	All visits	Descriptive
	Whole image capillary density %;	baseline	1, 3 and 6 months following Treatment 1	Treatment effect
	Inside disc capillary density %; Retinal peripapillary capillary density %		1, 3 and 6 months post-cellular therapy in both arms; 12 months post-cellular therapy in immediate cell/deferred sham arm	Effect of cellular therapy over time

7.3.2.4 Changes in Multifocal ERG

As a secondary outcome measure and an objective measure of macular function, multifocal ERGs will be performed. Table 6 outlines outcome analyses that will be performed for multifocal ERG. Categorical versions of continuous variables may also be explored.

Table 6: Multifocal ERG Outcomes			
Outcome Measure	Parameter	Timepoints	Analyses
Number of abnormal	Mean change from	All visits	Descriptive
Mean amplitude S.D.	baseline	1, 3 and 6 months following Treatment 1	Treatment effect
Number of abnormal latency hexagons Mean Latency S.D.		1, 3 and 6 months post- cellular therapy in both arms; 12 months post- cellular therapy in immediate cell/deferred sham arm	Effect of cellular therapy over time

7.3.2.5 Changes in Full-Field ERG

As a secondary outcome measure and an objective measure of global retinal function, the change in retinal function in the study eye based on full-field ERG will be assessed. Table 7 outlines outcome analyses that will be performed for full-field ERG. Categorical versions of continuous variables may also be explored.

Table 7: Full-field ERG Outcomes			
Outcome Measure	Parameter	Timepoints	Analyses
% Normal amplitude	Mean	All visits	Descriptive
for a-wave and b- wave under scotopic conditions	change from baseline	1, 3 and 6 months following Treatment 1	Treatment effect
Flicker amplitude % Normal amplitude for ERG+OP a-wave and b-wave under scotopic conditions		1, 3 and 6 months post- cellular therapy in both arms; 12 months post- cellular therapy in immediate cell/deferred sham arm	Effect of cellular therapy over time
% Normal latency for a-wave and b- wave under scotopic conditions	Mean change from baseline	All visits	Descriptive
% Normal amplitude for a-wave and b- wave under photopic conditions			
% Normal latency for a-wave and b- wave under photopic conditions			
Flicker latency			
% Normal latency of ERG + OP a-wave and b-wave under scotopic conditions			

7.3.2.6 Changes in Autofluorescence

As a secondary outcome measure, the change in autofluorescence (AF) in the study eye will be assessed. Table 8 outlines outcome analyses that will be performed for autofluorescence. Categorical versions of continuous variables may also be explored.

Table 8: Autofluorescence Outcomes			
Outcome Measure	Parameter	Timepoints	Analyses
Area of definite	Mean	All visits	Descriptive
Area of increased	baseline	1, 3 and 6 months following Treatment 1	Treatment effect
		1, 3 and 6 months post- cellular therapy in both arms; 12 months post- cellular therapy in immediate cell/deferred sham arm	Effect of cellular therapy over time

7.3.2.7 Changes in Fundus Photography and Fluorescein Angiography

As a secondary outcome measure and to evaluate for changes in retinal perfusion, fundus photography and fluorescein angiography (FA) will be performed throughout the study. Table 9 outlines outcome analyses that will be performed for fundus photography and fluorescein angiography outcomes. For fundus photography, a focused review of the degree of retinal and pre-retinal hemorrhage data will be performed to assess for patterns.

Table 9: Fundus Photography and Fluorescein Angiography Outcomes				
Modality	Outcome Measure	Parameter	Timepoints	Analyses
Fundus Photography	Degree of retinal hemorrhage by ETDRS/Networc zones	Count, percentage	All visits	Descriptive
	Degree of pigment changes by ETDRS/Networc zones			
	Degree of retinal fibrosis by ETDRS/Networc zones			
	Degree of NV by ETDRS/Networc zones			
	Degree of pre-retinal hemorrhage by ETDRS/Networc zones			
Fluorescein Angiogram	Foveal avascular zone integrity	Count, percentage	All visits	Descriptive

٦

	Table 9: Fundus Photography and Fluorescein Angiography Outcomes				
Modality	Outcome Measure	Parameter	Timepoints	Analyses	
	Area of non-perfusion	Mean change from	All visits	Descriptive	
	Within ETDRS Grid Area of non-perfusion within Networc Grid	baseline	1, 3 and 6 months following Treatment 1	Treatment effect	
			1, 3 and 6 months post-cellular therapy in both arms; 12 months post-cellular therapy in immediate cell/deferred sham arm	Effect of cellular therapy over time	
	Grade of capillary non- perfusion	Count, percentage	All visits	Descriptive	
	Number of	Mean change from	All visits	Descriptive	
	microaneurysms	baseline	1, 3 and 6 months following Treatment 1	Treatment effect within ETDRS grid and within Networc grid	
			1, 3 and 6 months post-cellular therapy in both arms; 12 months post-cellular therapy in immediate cell/deferred sham arm	Effect of cellular therapy over time within ETDRS grid and within Networc grid	
	Grade of telangiectatic vascular changes	Count, percentage	All visits	Descriptive	

